Details of Stable Glycerol Isotope Tracer studies with an OSTT: Participants will fast overnight, and drink 3 doses of D2O three times during the night with doses at 6-8PM, 10-11 PM and 2-3 AM as described previously in obese youth. The total D2O to be given (3 mL per kg of body water) is designed to raise body deuterium levels to 0.3% and was administered in three doses to maintain the steady state until the end of the study. Serum samples will be collected in the morning before the glycerol, and then throughout the OSTT, and VLDL TG separated and then enrichment in palmitate measured. By evaluating the incorporation of the D2O into palmitate, we will be able to assess the DNL expressed as a percentage of DNL. We will also measure the rate of gluconeogenesis by measuring the enrichment in serial plasma glucose samples.

The following morning at approximately 7:00AM, a 50 mg/kg of an oral C-glycerol tracer will be consumed mixed with water. Blood samples will be collected and at approximately 10AM, participants will consume a 75 gram glucose load with an additional 25 grams of fructose to stimulate hepatic de novo lipogenesis. Analysis of serum glucose isotopomers will be performed by our collaborator [name] at UT Southwestern, using NMR isotopomer analysis and pathway modeling software. Lipolysis will be modeled using FFA concentrations and whole body IR by a time modified version of the Matsuda model.

Using a metabolic cart and hood, resting VO2 (ml/kg/min) and VCO2 (ml/kg/min) measurements (REE) will be collected the morning of the OSTT prior to the start of the OSTT, and two more times during the OSTT. This is required to determine what portion of ingested carbohydrates are subject to oxidative and non-oxidative glucose disposal.

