Study diet: Variations in diet, activity and circadian rhythms affect metabolism^121. Therefore, OSTT studies will be performed in the AM, in the follicular phase where possible, preceded by 3 days of no strenuous physical activity. Participants will be advised to eat a typical diet for the 3 days preceding the study. On the day of study, they will have a snack and dinner selected from limited choices on the Children's hospital carbohydrate counting diet plan, with at least 20 grams of carbs in the snack and 40 grams of carbs for dinner. Participants will ingest their study drink (amino acid or placebo) in the morning of the day of admission, and then after the MRI with their snack.

**Note:** Participants will stop taking placebo or EAA supplements after completion of overnight visit for approximately 4 weeks (washout period). Then participants will crossover to EAA or placebo. The pharmacy will dispense the proper supplement, since study staff and participant will be blinded. The participant will be scheduled for Visits 4 and 5 after being on placebo or EAA supplements for 4 weeks.

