## 6. Standard Diet

*Description:* A dinner and snack will be provided during the overnight visit, selected from limited choices on the Children's Hospital cafeteria carbohydrate counting diet plan, with at least 20 grams of carbs in the snack and 40 grams of carbs for dinner.

*Risk:* None

*Justification/Minimization:* Variations in diet, activity and circadian rhythms affect metabolism .

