## **IV. Potential Scientific Problems:**

### **Limitation of Method Development:**

The protocol as described includes an OSTT with an oral tracer will be conducted in all participants. The specific points that are to be evaluated are listed below:

- 1) Measurement of Hepatic Substrate flux in youth during fasting.
  - a. Purpose: Assess hepatic substrate flux in youth looking at shifts from pentose phosphate pathway (PEP), TCA cycle and fatty acid synthesis
  - i. Rational: utilizing and oral glycerol model with NMR isotopomer analysis is a newer technique. We have validated the timing with an OSTT in youth. However, this relies on consistent OSTT responses. When we anticipate that the response to the OSTT may change, the timing and thus results would vary, and we are thus better off using a fasting model. This has been done in adults, but not in our youth.
  - ii. Measurement: NMR isotopomer analysis with pathway flux calculations and modeling in the fasting state
  - iii. Revision plan if model not correct: 1) increase the amount of tracer given 2) increase the frequency of blood draws in the later sampling period.

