## VII. Data Analysis Plan:

### Overall Project Statistical Plan:

Sample size analysis: Sample size is based on the power to detect a change in IHTG with treatment with EAA as compared to placebo (primary endpoint). Assuming a 2-sided  $\alpha=0.05$ , 20 participants provides 86% power to detect a change of 2.8% in IHTG, assuming a 3.9% standard deviation of change, which corresponds to a correlation of 0.8 between repeated measures. For Aim secondary measures, a 2 sample size of 20 gives 99% power to detect a change of 14.4 mg/dL in 2 hour OSTT glucose and 81% power to detect a change of 1.8 in HOMA-IR, assuming a standard deviation of 14.4 mg/dL and 2.7, respectively. Estimates of effect size and variability were conservatively estimated from the PI's extensive pilot data.

Analysis plan: No interim analyses are planned. Prior to the start of any formal analyses, unusual values that need to be queried, patterns of missing values, and whether their distributions are non-Gaussian will be identified. Demographic and clinical characteristics will be summarized with descriptive statistics. Analyses will follow the "intent-to-treat" principle so that study hypotheses are tested under realistic conditions in which not all participants adhere to the intervention. For the primary outcome, we will compare IHTG with and without EAA treatment using a paired t-test or a Wilcoxon signed rank test. Similar analyses will be used for secondary outcomes (2 hour OSTT glucose, HOMA-IR, metabolomics markers, proportion of direct/indirect glucose, EAA concentrations). Linear models will be used to identify the variables that are associated with change in IHTG, such 2 hour OSTT glucose, HOMA-IR, metabolomics markers, etc.

All measures will be adjusted for OSA status (yes/no) and/or severity of AHI.

Secondary outcomes include a Pearson correlation test of potentially related variables followed by targeted multiple regression to assess the relationship between hepatic fat and adipose IR, PEP, TCA, TG synthesis pathways.

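### Nothing requires a girl's Visit 5 evening meal to match her Visit 3 meal, which adds avoidable within-girl noise to the fasting DNL, gluconeogenesis and hepatic-flux comparisons

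*Combined protocol and SAP*

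**What the plan says.** Each girl is given a snack and a dinner on the evening before the tracer and sugar-tolerance tests. The Study diet paragraph under Visit 3 specifies them "with at least 20 grams of carbs in the snack and 40 grams of carbs for dinner". The Standard Diet item in section III.D repeats those minimums and describes the food as "selected from limited choices on the Children's Hospital cafeteria carbohydrate counting diet plan". Neither place sets a maximum. Both justify the provision by noting that diet, among other factors, influences metabolism. Visit 5, the second-period counterpart, is described only by a cross-reference to Visit 3.

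The tracer details under Visit 3 give deuterated water that same evening and night, with "doses at 6-8PM, 10-11 PM and 2-3 AM". The glycerol tracer follows at about 7 AM while the girl is fasting, and the sugar drink (75 g glucose plus 25 g fructose) at about 10 AM. Palmitate enrichment, from which DNL is read, is sampled before the glycerol and then through the sugar test.

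The Data Analysis Plan (section VII) compares treatments with a paired t-test or Wilcoxon signed rank test, and uses similar analyses for secondary outcomes. The adjustments it names are sleep apnoea status or severity and, for the sugar-test indices, activity and sleep. Evening carbohydrate is not among them.

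**The concern.** A crossover with 20 girls relies on each girl being her own control, so test conditions should differ between her two periods as little as is practical. Here the meal eaten close to the start of labelling may differ by any amount above the minimums. The protocol treats carbohydrate as a driver of DNL: the fructose in the sugar drink is there to stimulate it, and the Lifestyle Prescription section warns that variable sugary-drink intake may affect results.

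At stake is the mechanistic half of both aims. Aim 1 claims that liver fat falls through lower DNL, and Aim 2 that diabetes risk falls through altered gluconeogenesis and its precursors. Extra within-girl variation in those measures makes a true mechanism harder to show.

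**Working it through.** **1. What is fixed and what is left open**

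| Condition | Same at Visits 3 and 5? |
|---|---|
| Deuterated water time windows, 50 mg/kg glycerol, 75 g + 25 g sugar drink | Yes, by shared procedure |
| Overnight fast, morning testing, 3 days without strenuous activity | Yes, by shared procedure |
| Snack and dinner source | Yes: provided, limited menu |
| Snack and dinner items and amounts | Minimums only (20 g + 40 g = 60 g); no maximum, no repeat rule |

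The possible gap cannot be read from the protocol. If dinners could run up to 120 g (an assumption), a girl's two dinners could differ by anything from 0 to 120 − 40 = 80 g, against the 75 + 25 = 100 g sugar load. No figure converts grams of evening carbohydrate into a change in DNL, so this goes no further.

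**2. Which endpoints are exposed**

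- Primary liver fat by MRI: not exposed. Overall Study Design puts the scan in the afternoon, after a fast of at least 4 hours and before the evening meal.
- Fasting DNL, fasting gluconeogenesis and fasting glycerol flux: exposed. They are measured the next morning.
- DNL samples after the sugar drink: less exposed, since the same load precedes them at both visits.

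**3. The plan's power figures, reproduced**

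The section VII inputs are N = 20 pairs and two-sided alpha 0.05. Power comes from the noncentral t distribution with 19 degrees of freedom and noncentrality (change / SD of change) × √20.

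- Liver fat: 2.8 / 3.9 = 0.718, giving 86.1%. The plan says "20 participants provides 86% power to detect a change of 2.8% in IHTG".
- 2-hour glucose: 14.4 / 14.4 = 1.0, giving 98.9%. The plan "gives 99% power to detect a change of 14.4 mg/dL in 2 hour OSTT glucose".
- HOMA-IR: 1.8 / 2.7 = 0.667, giving 80.7%, against a stated 81%.

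All three reproduce. No effect, SD or power is stated for DNL, gluconeogenesis or flux.

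**4. What extra noise would do (illustration)**

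Suppose unmatched meals add a fraction v to the variance of the within-girl difference. The SD of change is then multiplied by √(1 + v). The standardised effects 0.667 and 1.0 are borrowed from HOMA-IR and 2-hour glucose. They are not estimates for the mechanistic endpoints.

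| v (assumed) | Power at 0.667 | Power at 1.0 |
|---|---|---|
| 0 | 80.7% | 98.9% |
| 10% | 76.9% | 98.1% |
| 25% | 71.6% | 96.6% |
| 50% | 63.7% | 93.3% |
| 100% | 51.6% | 85.1% |

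**5. Noise or bias**

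If meal choice does not depend on treatment, randomised order makes the meal difference average zero in the EAA-minus-placebo contrast. A systematic drift between periods was checked by simulation (50,000 runs per setting). The second-period value was shifted by 0.5 or 1 SD of the difference in 4, 10 or all 20 girls.

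- Mean bias was about 0.
- Type I error was 5.0–5.1% with simple randomisation and 0.6–4.9% with a 10:10 split.
- Power at 0.667 fell from 80.7% to between 79% and 51%.

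A single trial with unequal sequences can still carry part of such a drift. With a 13:7 split and all girls shifted, the fraction is (13 − 7) / 20 = 30%. A split at least that uneven has probability 26% under simple randomisation.

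**The case against.** The strongest reply is that the plan already controls most of what matters. The meal is provided from a short menu, the overnight fast is monitored, the tracer and sugar drink are fixed, and both visits follow one written procedure. The protocol does not say the meals will differ; it only omits a rule that they match. It also considered tighter dietary control, naming a provided diet for three days before the studies as an alternative, and it assesses dietary intake. All of this stands. It makes the gap a matter of precision in secondary endpoints.

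Three stronger readings are tempting and are not supported.

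- *Treatment is confounded with test conditions.* Order is randomised, and staff and participants are blinded. The one route to systematic bias is that the supplement changes what a girl chooses to eat. The second study drink that day is taken with the snack, so this is conceivable, but the protocol says nothing about it either way.
- *The labelled lipid is the lipid made from that dinner.* Deuterated water is given in three doses to hold a steady state to the end of the study, and sampling continues through a fixed sugar load. The dinner is one influence, mainly on the fasting samples.
- *The method may change partway through a girl's participation.* The section on limitations of method development does contain a "Revision plan if model not correct: 1) increase the amount of tracer given 2) increase the frequency of blood draws in the later sampling period". That clause concerns the fasting glycerol isotopomer model and leaves deuterated water untouched, so it does not bear on DNL or on gluconeogenesis measured with it. It gives no timing. With even accrual of 20 girls over 2.5 years (about 130 weeks) and about 8 weeks between Visits 3 and 5, roughly 20 × 8 / 130 = 1.2 girls would be between visits on any date. Holding those girls to a version already judged incorrect would be a trade-off, so it is not a clear improvement.

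**Conclusion.** The point holds as a cheap improvement to the secondary mechanistic endpoints. The evening meal has minimums but no matching rule, the protocol's own rationale says that diet matters, and the analysis does not account for the meal. The consequence to expect is avoidable within-girl noise in the fasting DNL, gluconeogenesis and hepatic-flux comparisons.

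Its size cannot be computed from the protocol. The power table rests on assumed variance increases and borrowed effect sizes, so it shows only how sensitive a 20-pair comparison could be. The conclusion that this is noise rests on randomised, blinded order and on meal choice not depending on the supplement. The primary liver-fat result and its 86% power are not in question here.

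**What to change.** Add one sentence to the Study diet paragraph under Visit 3 and to the Standard Diet item in section III.D: *The snack and dinner items and amounts eaten at Visit 3 are recorded, and the same items and amounts are served at Visit 5.*

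The cost is a meal record kept from Visit 3 and less menu choice for the girl at Visit 5. It needs no extra visit, sample or participant, and no change to the primary analysis.

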#### **VISIT 4 (MRI VISIT)**

See Visit 2 Description.

#### **VISIT 5 (ORAL GLYCEROL TRACER WITH D20 AND ORAL SUGAR TOLERANCE TEST)**

See Visit 3 Description.

Purpose for lab test to be drawn:

OSTT Labs	Purpose
Lipids and glycerol samples for tracer analysis	Determination of hepatic metabolism flux
Glucose	Determination of IR
Insulin	Determination IR
FFA	Measure of lipolysis
Glycerol	Measure of lipolysis
Glucagon	Gut hormone known to influence hepatic IR
GLP-1	Gut hormone known to influence hepatic IR
CRP	Marker of inflammation, know to effect IR
Leptin	Gut hormone known to influence hepatic IR
Adiponectin	Adipokine thought to influence adipose IR
Estradiol	Known to effect IR and HDNL
Progesterone	Demonstrate the participant is in the follicular phase of cycle, required for publication
Metabolomics	Correlation with hepatic metabolism flux
1 sample for genetic analysis	Measure for common polymorphisms associated with hepatic steatosis 
Stored blood	Future markers of glucose and fat metabolism, CVD or hormones related to PCOS

Purpose for questionnaires being done:

Questionnaire	Description	Study Validity
Adolescent Sleep Hygiene Scale	Measurement of sleep patterns/habits	Cronbach's alpha ranges from .46-.74; total scale alpha = .80  LeBourgeois et al. 2005. The Relationship Between Reported Sleep Quality and Sleep Hygiene in Italian and American Adolescents

Center for Epidemiological Studies Depression (CES-D)	Measuring for depression	See Table 3 below, adapted from:  Stockings et al. 2015. Symptom screening scales for detecting major depressive disorder in children and adolescents: A systematic review and meta-analysis of reliability validity and diagnostic utility
Cleveland Adolescent Sleepiness Questionnaire	Measurement of sleepiness during a typical week	alpha = 0.89  Spilsbury et al. 2007. The Cleveland Adolescent Sleepiness Questionnaire: A New Measure to Assess Excessive Daytime Sleepiness in Adolescents
SDQ: Strengths and Difficulties Questionnaire	Behavioral screening questionnaire	The internal reliability of the various self report scales was assessed using Cronbach's alpha coefficient. This was 0.82 for the total difficulties, 0.75 for emotional symptoms, 0.72 for conduct problems, 0.69 for hyperactivity, 0.65 for prosocial behaviour, and 0.61 for peer problems.  Goodman et al. 2003. The Strengths and Difficulties Questionnaire: a pilot study on the validity of the self-report version
Sleep Disturbances Scale for Children	Gain understanding of sleep-wake rhythm and any problems in sleep behavior	Internal consistency ranged from .71-.79  test-retest reliability $r = .71$  Bruni et al. 1996. The Sleep Disturbance Scale for Children (SDSC) Construct ion and validation of an instrument to evaluate sleep disturbances in childhood and adolescence
3DPAR: Activities Scale	Measuring activity in the 3 days previous as a typical activity score	Interrater and test-retest reliability was 0.99 and 0.98, respectively ( $P < 0.01$ ). The correlation between relative energy expenditure from the PDPAR ( $\text{kcal.kg}^{-1}.\text{l.d}^{-1}$ ) and pedometer and Caltrac counts was 0.88 ( $P < 0.01$ ) and 0.77 ( $P < 0.01$ ), respectively. The correlation between percentage heart rate range ( $\text{HR}_{\text{max}}\text{-HR}_{\text{rest}}$ ) and mean energy expenditure from the PDPAR was 0.53 ( $P < 0.01$ ). The correlation between 1-min heart rates $> 50\%$ HRR sustained for 20 min and the number of 30-min blocks with a relative energy expenditure of at least four metabolic equivalent tasks (MET) was 0.63 ( $P < 0.01$ ). The PDPAR provides valid and reliable estimates of physical activity and also accurately identifies bouts of moderate to vigorous activity.  Weston et al. 1997 Validation of an instrument for measurement of physical activity in youth
Food Frequency Questionnaire	Measuring typical food intake over	The mean correlations, adjusted for measurement error, of food groups and

	previous seven days.	
nutrients between the FFQ and true usual intake were 0.41 and 0.38, respectively, with 57 % of food groups and 70 % of nutrients exhibiting correlations >0.35. Correlations were high for low-fat dairy (0.80), sugar-sweetened beverages (0.54), cholesterol (0.59) and saturated fat (0.51), while correlations were poor for high-fibre bread and cereal (0.16) and folate (0.11). Reliability of FFQ intake based on two FFQ administrations was also reasonable, with 54 % of Pearson correlation coefficients <math>\geq 0.5</math>. Reliability was high for low-fat dairy (0.7), vegetables (0.6), carbohydrates, fibre, folate and vitamin C (all 0.5), but less than desirable for low-fat poultry and high-fibre bread, cereal, rice and pasta (0.2-0.3).
 
Liese et al. 2015 Relative validity and reliability of an FFQ in youth with type 1 diabetes
 
First described in 2006:
 
Mayer-Davis et al. 2006. Search FFQ Dietary Intake among Youth with Diabetes: The SEARCH for Diabetes in Youth Study

Optional 7 Day Food Log	Optional record of 7-day diet to aid in food recall. Added per participant request to help fill out food frequency questionnaire.	N/A
Actigraphy Daily Sleep Diary	Recording bedtime/wake time during actigraphy. Needed to corroborate watch collected data	N/A

Table 3

Validation evidence for the Center for Epidemiologic Studies Depression Scale (CES-D) in child and adolescent samples.

Source	N	Age and Gender (% m, % f)	Sample (location)	Scale name (no. of items)	Reliability	Criterion	Cutoff	Sensitivity	Specificity	PPV	NPV	AUC
Clinical												
Logsdon and Myers (2010)	59	13–18 (0, 100)	Adolescent mothers at 4–6 weeks postpartum (USA)	CES-D (20)	$\alpha=0.84$	K-SADS- PL	16	0.7	0.52	0.25	0.12	0.62
Aebi et al. (2009)	140	Mean: 15.5 (33, 67)	Adolescents diagnosed with major depressive disorders (Switzerland)	CES-D (20)	$\alpha=0.83$	Clinical interview	21	0.86	0.86	–	–	0.94
Non- clinical												
Betancourt et al. (2012)	367	10–17 (33, 67)	Children and adolescents (Rwanda)	CES-DC (20)	$\alpha=0.86$	MINI-KID	$\geq 30$	0.82	0.72	–	–	0.83
Cuijpers et al. (2008)	1392	14–16 (52, 48)	Adolescents (Netherlands)	CES-D (20)	$\alpha=0.93$	MINI	22	0.9	0.74	–	–	0.90
Thrane et al. (2004)	213	9–16 (54, 46)	Adolescents from three American Indian reservations (USA)	CES-D (20)	$\alpha=0.80$	–	–	–	–	–	–	–
Yang et al. (2004)	2440	12–16 (52, 48)	Adolescents (Taiwan)	CES-D (20)	$\alpha=0.9$	K-SADS-E	90 th % tile	0.41	0.9	–	–	0.9
Prescott et al. (1998)	556	Mean: 16.8	Adolescent students from grades 9–12 (USA)	CES-D (20)	–	DISC	16	0.79	0.74	0.24	0.96	0.74
Garrison et al. (1991)	1231	12–14 (100, 0)	Child and adolescent boys from school sample (USA)	CES-D (20)	$\alpha=0.81$	K-SADS-P	12	0.85	0.49	0.16	0.98	0.61
Garrison et al. (1991)	1234	12–14 (0, 100)	Child and adolescent girls from a school sample (USA)	CES-D (20)	$\alpha=0.86$	K-SADS-P	22	0.83	0.77	0.32	0.98	0.77
Roberts et al. (1991)	1710	14–18 (47, 53)	Adolescents of nine senior high schools (USA)	CES-D (20)	$\alpha=0.89$	K-SADS	24	0.84	0.75	0.08	0.99	–
Roberts et al. (1991)	804	14–18 (100, 0)	Adolescent male sample of nine senior high schools (Roberts et al., 1991; USA)	CES-D (20)	–	K-SADS	22	–	–	–	–	0.87
Roberts et al. (1991)	906	14–18 (0, 100)	Adolescent female enrolment of nine senior high schools (Roberts et al., 1991; USA)	CES-D (20)	–	K-SADS	24	–	–	–	–	0.83
Fendrich et al. (1990)	220	12–18	Children and adolescents at risk for depression according to their parents' diagnosis (USA)	CES-DC (20)	$\alpha=0.89$	K-SADS-E	$\geq 16$	0.71	0.62	0.15	0.96	–

Note: N=Number of participants in the study sample. PPV=Positive predictive value. NPV=Negative predictive value. AUC=Area under the curve analysis. CES-D=Center for Epidemiologic Studies Depression Scale. CES-DC=Center for Epidemiologic Studies Depression Scale Child Version.  $\alpha$ =Cronbach's alpha reliability co-efficient. K-SADS-PL: The Schedule for Affective Disorders and Schizophrenia for School-Age Children – Present and Lifetime version. MINI-KID: The Mini-International Neuropsychiatric Interview. MINI: The Mini-International Neuropsychiatric Interview for children. K-SADS: The Schedule for Affective Disorders and Schizophrenia for School-Age Children. K-SADS-E: The Schedule for Affective Disorders and Schizophrenia for School-Age Children – Epidemiological version. DISC: The National Institute of Mental Health Diagnostic Interview Schedule for Children. K-SADS-P: The Schedule for Affective Disorders and Schizophrenia for School-Age Children Present Episode version.

## LIFESTYLE PRESCRIPTION

1) At the time of screening, all participants will receive standard lifestyle recommendations including the reduction of liquid carbohydrate and portion control. We will not perform extensive counseling at this time as major changes in diet could affect the results. However, variability in the consumption of sugar sweetened beverage may affect results, and thus we will discourage these in all participants. Further this is the first step of standard lifestyle counseling for this population.

2) The final visit will conclude with education regarding the importance of physical activity, diet and lifestyle modification to mediate the risks associated with sedentary lifestyle and an exercise prescription designed to increase physical activity. The information at this visit will build on the previous education, and be personalized to include the basal metabolic rate calculations and specific dietary recommendations based on the food frequency survey. The exercise information and prescription are the standard of care used in our Children's Hospital Colorado Pediatric Metabolic Syndrome Clinic, designed by the Children's Hospital Colorado Pediatric Exercise Physiologist. Families will be provided with standard information about follow up care with their primary care provider and contact information for Children's Hospital Colorado Diabetes and Child Health Clinics if needed regarding any abnormal study findings. In addition, the participant/family will be provided with copies of their study lab results, DEXA scan and physical activity monitoring. A results letter will be provided to the family within 6 months of completion of the study about clinically relevant results obtained during the study. Participants will be encouraged to contact study staff with questions regarding the results letter.

